7.1.2 Clinical Investigation Plan (CIP) Deviations

All protocol deviations will be presented in the listings.

7.1.3 **Analysis Sets**

Intention to Treat (ITT) Population

The primary study population is the Intention to Treat (ITT) population, which consists of all randomized subjects.

Per Protocol (PP) Population

The Per Protocol (PP) population will include all randomized subjects who complete the trial without any major deviations, have worn the sensor for both Arms (SAP and HCL) and have used Automode (HCL only) for \geq 80% of the time, pump usage (HCL only) of at least 80% and sensor usage (HCL only) of at least 60% during the study period. CSII and MDI control arms need to have at least 60% sensor usage during the blinded sensor wear time. In addition, those subjects who take steroids after randomization will be excluded from PP population. Primary effectiveness endpoints and key secondary endpoints will be evaluated for PP Population.

Safety Population

The Safety Population will be all enrolled subjects.

2-6 Years of Age Population (670G and 770G only)

This analysis set will include subjects 2-6 years of age who used HCL therapy (670G or 770G). Descriptive summary statistics will be provided.

This document is electronically controlled *Medtronic Controlled Information* 056-F286, Statistical Analysis Plan Template

CEP304 Statistical Analysis Plan Revision 3.0 Page 15 of 34 Medtronic

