- End of Study Period and Start of Continuation period.
- Start CGM with Guardian Sensor (3)

b. MDI Cohort

Visit 4: Day 0

Visit 5: Follow up Office Visit 7-21 days after Visit 4

Visit 6A: Follow up Telephone Visit - 1 Day after Visit 5

Visit 6B: Follow up Telephone Visit - 2 Days after Visit 5

Visit 6C: Follow up Telephone Visit - 14 Days (± 5 days) after Visit 5

Visit 6D: Follow up Office Visit - 25 Days after Visit 5 (± 5 days)

Visit 6E: Follow-up Telephone Visit - 35 Days (+1 day) after Visit 5

Visit 7: Follow up Office Visit - 76 days after Randomization (-2 days)

- Blinded CGM Start
- o 14 days of sensor wear before 90 Day study period visit.

Visit 8A: Follow up Office Visit – 90 Days after Randomization (+14 days)

Blinded CGM Return

Visit 8B: Follow up Office Visit - 166 days after Randomization (-14 days)

- Blinded CGM Start
- o 14 days of sensor wear before 180 Day study period visit.

Visit 9: Follow up Office Visit – 180 Days after Randomization (+14 days)

CEP304DOC Revision H Page 97 of 182 **Medtronic**

- Blinded CGM Return
- o End of Study Period and Start of Continuation period.
- Start study pump

c. SAP Cohort:

Visit 4: Day 0

Visit 4A: Follow up Telephone visit - 2-3 days after Visit 4

Visit 5: Follow-up Office Visit - 7-21 days after Visit 4

o Pump and Sensor adjustments

Visit 6A: Follow-up Telephone Visit (option of office visit) – 1 Day after Visit 5

Visit 6B: Follow-up Telephone Visit (option of office visit) - 2 Days after Visit 5

Visit 6C: Follow-up Telephone Visit 7 days after Visit 5 (+3 days)

Visit 7A: Follow-up Telephone Visit - 14 Days after Visit 5 (± 3 days)

Visit 7B: Follow-up Telephone Visit - 21 Days after Visit 5 (± 3 days)

Visit 7C: Follow-up Office Visit - 30 Days after Visit 5 (± 5 days)

Visit 7D: Follow-up Telephone Visit - 45 Days (± 7 days) after Visit 5

Visit 8: Follow-up Office Visit - 90 Days after **Randomization** (± 10 days)

Visit 9: Follow-up Office Visit - 180 Days after Randomization (± 10 days)

- End of Study Period and Start of Continuation period
- Auto Mode is enabled and activated.

Continuation Period:

HCL Arm:

Visit 10: Follow up Office Visit – 1 to 14 days after Visit 9

Visit 11: Follow up Office Visit – 15 to 30 days after Visit 9

CEP304DOC Revision H Page 98 of 182 **Medtronic**

Visit 12: Follow up Office Visit - 270 Days after Randomization (+/- 21 days)

Visit 13: Follow up Office Visit - 365 Days after Randomization (+/- 21 days)

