o End of Continuation Period and End of Study

Control Arm

a. CSII Cohort:

Visit 10A: Follow up Telephone visit - 2-3 days after sensor start

Visit 10B: Follow up Office Visit 7-21 days after Visit 9

Auto Mode is enabled and activated.

Visit 10C: Follow up Telephone Visit (option of office visit) – 1 Day after Visit 10B

Visit 10D: Follow up Telephone Visit (option of office visit) – 2 Days after Visit 10B

Visit 10E: Follow-up Telephone Visit – 5 Days (± 1 day) after Visit 10B

Visit 11A: Follow up Office Visit - 14 Days after Visit 10B (±3 days)

Visit 11B: Follow-up Telephone Visit - 21 Days (±3 days) after Visit 10B

Visit 11C: Follow up Office Visit - 30 Days after Visit 10B (±5 days)

Visit 11D: Follow-up Telephone Visit - 45 Days (±7 days) after Visit 10B

Visit 12: Follow up Office Visit - 270 Days after Randomization (+/- 21 days)

Visit 13: Follow up Office Visit - 365 Days after Randomization (+/- 21 days)

o End of Continuation Period and End of Study

b. MDI Cohort:

Visit 9A: Follow up Office Visit – 14-30 days after Visit 9

- Start CGM with Guardian Sensor (3)
- This visit should occur between 14 and 30 days after pump start.

Visit 10A: Follow up Telephone visit - 2-3 days after sensor start

Visit 10B: Follow up Office Visit 7-21 days after Visit 9A

CEP304DOC Revision H Page 99 of 182 **Medtronic**

- o Patient has been wearing CGM for at least 4 days before enabling Auto Mode
- Auto Mode is enabled and activated.

Visit 10C: Follow up Telephone Visit (option of office visit) – 1 Day after Visit 10B

Visit 10D: Follow up Telephone Visit (option of office visit) – 2 Days after Visit 10B

Visit 10E: Follow-up Telephone Visit – 5 Days (± 1 day) after Visit 10B

Visit 11A: Follow up Office Visit - 14 Days after Visit 10B (±3 days)

Visit 11B: Follow-up Telephone Visit – 21 Days (± 3 day) after Visit 10B

Visit 11C: Follow up Office Visit - 30 Days after Visit 10B (±5 days)

Visit 11D: Follow-up Telephone Visit – 45 Days (± 7 day) after Visit 10B

Visit 12: Follow up Office Visit - 270 Days after Randomization (+/- 21 days)

Visit 13: Follow up Office Visit - 365 Days after Randomization (+/- 21 days)

End of Continuation Period and End of Study

c. SAP Cohort:

Visit 10A: Follow up Telephone Visit (option of office visit) – 1 Day after Visit 9

Visit 10B: Follow up Telephone Visit (option of office visit) – 2 Days after Visit 9

Visit 10C: Follow-up Telephone Visit – 5 Days (± 1 day) after Visit 9

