7.2 General Methodology

All data from the time of screening until the end of the study will be collected either on eCRFs or electronically by uploading the various devices. Data and analysis will be summarized in a Clinical Study Report.

All endpoints are hierarchically ordered and will be evaluated in the fixed sequence from primary endpoints to secondary endpoints. Unless the primary endpoints hypotheses are rejected, secondary endpoints will not be tested.

Effectiveness endpoints will be evaluated during the 6 month study period by individual Cohort (CSII, MDI or SAP), stratified by A1C;

Group 1: Baseline A1C > 8%

Group 2: Baseline A1C ≤ 8%

[figure not shown]
The comparison of HCL arm vs. Control arm will be performed. For SG-based comparison between HCL vs Control analyses, two weeks of CGM data collected at 3 month visit and 6 month visits will be used.

Please note: Only descriptive summary statistics will be provided for 2-6 years old who used HCL therapy (670G or 770G).

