- 3. Cengiz et. al: Severe hypoglycemia and diabetic ketoacidosis among youth with type 1 diabetes in the T1D Exchange clinic registry. Pediatr Diabetes. 2013 Sep;14(6):447-54.
- 4. MDT on file: Statistical Analysis Plan (SAP) for CEP304, 056-F286

Co-Primary Effectiveness Endpoints

The primary effectiveness endpoints consist of one-primary endpoint for each group.

Group 1 – Baseline A1C > 8%: Change in A1C (Δ A1C)

The primary effectiveness endpoints for the baseline A1C > 8% group is change in A1C from baseline to end of six-month treatment period, defined as A1C measured at the six-month treatment visit minus A1C measured at the randomization visit. The goal is to show superiority of the HCL Arm compared to the Control Arm in reducing A1C from baseline to end of six-month treatment period.

The hypothesis is mathematically expressed as:

H₀: μ (HCL) $\geqslant \mu$ (Control)

Ha: $\mu(HCL) < \mu(Control)$

CEP304 Statistical Analysis Plan Revision 3.0 Page 23 of 34 Medtronic

where $\mu(HCL)$ is the mean of change in A1C (%) with the HCL Arm, $\mu(Control)$ is the mean of change in A1C (%) with the Control Arm.

Group2 - Baseline A1C ≤ 8%: Time in Hypoglycemic Range

The primary effectiveness endpoint for the baseline A1C \leq 8% group is the time with SG below 70 mg/dL (3.9mmol/L) during the six-month study period, defined as percentage of SG below 70 mg/dL (3.9mmol/L) out of total number of available SG readings. The goal is to show superiority of the HCL Arm compared to the Control Arm in reducing daily time in hypoglycemic range. The hypothesis is mathematically expressed as:

Ho:
$$\mu(HCL) \ge \mu(Control)$$

Ha:
$$\mu(HCL) < \mu(Control)$$

where $\mu(HCL)$ is the subject mean of time with SG below 70 mg/dL (3.9mmol/L) in the HCL Arm, $\mu(Control)$ is the subject mean of time with SG below 70 mg/dL (3.9mmol/L) in Control Arm.

Key Secondary Effectiveness Endpoints

Group 1 – Baseline A1C > 8%: Time in Hypoglycemic Range

The key secondary effectiveness endpoint for the baseline A1C > 8% group is the time with SG below 70 mg/dL (3.9mmol/L) during the six-month study period, defined as percentage of SG below 70 mg/dL (3.9mmol/L) out of total number of available SG readings. The goal is to show non-inferiority (with a non-inferiority margin of 2%) of the HCL Arm compared to the Control Arm. The hypothesis of non-inferiority is mathematically expressed as:

H₀:
$$\mu(HCL) \ge \mu(Control) + 2\%$$

Ha:
$$\mu(HCL) < \mu(Control) + 2\%$$

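### Per-protocol membership appears to depend on the continuation period to day 365, although the endpoints analysed on that set end at Visit 9 (day 180)

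*SAP*

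**What the plan says.** SAP 7.1.3 states that the PP population "will include all randomized subjects who complete the trial without any major deviations". Protocol 19.1.5 has the same clause. Both then list usage conditions. In the SAP the list ends with a time limit: Auto Mode for at least 80% "of the time, pump usage (HCL only) of at least 80% and sensor usage (HCL only) of at least 60% during the study period". The protocol's shorter list has no time limit. Both documents add that "those subjects who take steroids after randomization will be excluded from PP population", with no end date.

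On use, both say: "Primary effectiveness endpoints and key secondary endpoints will be evaluated for PP Population". SAP 7.2 places those endpoints in the randomized half year: "Effectiveness endpoints will be evaluated during the 6 month study period by individual Cohort". Change in A1C is "defined as A1C measured at the six-month treatment visit minus A1C measured at the randomization visit" (SAP 7.9), and the sensor-glucose endpoints use the CGM collected at the 3-month and 6-month visits (SAP 7.2).

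Protocol 10.3 sets Visit 9 at day 180 and labels it the end of the study period and the start of the continuation. Visit 13 is at day 365 ± 21 and is labelled "End of Continuation Period and End of Study". Between the two visits all subjects use HCL.

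**The concern.** If completing the trial means reaching Visit 13, PP membership for a finished six-month comparison is decided partly by events after the outcome was measured. A subject who complied fully through Visit 9 would leave the PP analysis for withdrawing, having a major deviation or taking a steroid during the continuation. One DKA episode would do the same, because protocol 11.1 withdraws the subject whatever the arm or period.

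A PP set is meant to isolate subjects who followed the assigned treatment while it was being compared. Later events do not bear on that. After Visit 9 the arms are also in different situations. The HCL arm continues its therapy, while controls start a new one; MDI controls start a pump, then CGM, then Auto Mode. Later losses therefore need not be alike in the two arms. At stake is how the PP results for the co-primary endpoints and the two non-inferiority key secondary endpoints are interpreted, and whether two programmers working from the same text would build the same set.

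**Working it through.** **Step 1. Which visit is completion?** The definition names none, so other places have to be compared.

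- Protocol 10.3: only Visit 13 carries the end-of-study label. Visit 9 ends the study period.
- Protocol 10.3, early withdrawal: subjects who leave before the last scheduled visit complete the Visit 13 requirements, so early exit is judged against Visit 13.
- Protocol 18.2: where six months is meant, the interim-analysis trigger says so explicitly.
- Protocol Table 6: first subject enrolled at 70 days and completed at 15 months; last subject enrolled at 55 to 57 months and completed at 69 months.

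Table 6 can be checked against the visit schedule, at 30.4375 days per month and with a run-in of 14 to 60 days:

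| Quantity | Calculation | Months |
|---|---|---|
| First subject, enrolled to completed | 15 − 70/30.4375 | 12.7 |
| Last subject, enrolled to completed | 69 − 57 to 69 − 55 | 12 to 14 |
| Enrollment to Visit 9, nominal | (14 + 180)/30.4375 to (60 + 180)/30.4375 | 6.4 to 7.9 |
| Enrollment to Visit 9, latest window (day 194) | (60 + 194)/30.4375 | 8.3 |
| Enrollment to Visit 13, nominal | (14 + 365)/30.4375 to (60 + 365)/30.4375 | 12.5 to 14.0 |
| Enrollment to Visit 13, with windows | (14 + 344)/30.4375 to (60 + 386)/30.4375 | 11.8 to 14.7 |

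Table 6 agrees with Visit 13. It does not agree with Visit 9, even with the 21 extra run-in days allowed for repeating blinded CGM: (81 + 194)/30.4375 = 9.0 months.

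**Step 2. How long after the endpoint does membership stay open?** Nominally 365 − 180 = 185 days, which is 185/365 = 51% of follow-up. Visit 9 falls between day 170 (HCL and SAP-control windows) and day 194 (CSII and MDI controls), and Visit 13 between day 344 and day 386. The range is therefore 344 − 194 = 150 to 386 − 170 = 216 days.

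**Step 3. How many subjects could be affected?** The readable text gives no continuation dropout rate. It does give a withdrawal rule (one DKA, protocol 11.1) and a ceiling for the DKA rate (4 per 100 patient-years in the HCL arm, SAP Table 1). Assume a constant rate, applied to both arms because all are then on HCL:

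- t = 185/365.25 = 0.5065 years
- P(at least one DKA) = 1 − exp(−0.04 × 0.5065) = 2.0%
- 0.0201 × 70 = 1.4 per arm and A1C group; × 140 = 2.8 per arm; × 280 = 5.6 per cohort

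The non-zero reference rates in the same table, 0.68 to 9.9 per 100 patient-years, give 0.3% to 4.9%. The upper end is a youth registry rate, and protocol 18.2 itself notes that registry rates exceed those in the clinical studies.

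**Step 4. Effect on the PP estimate.** If losses are equal and uninformative there is no bias, only lost precision. At an assumed further loss of 5% to 10% (not in the documents), 3.5 to 7 of 70 go, and the standard error rises by a factor of 1/√0.95 = 1.026 to 1/√0.90 = 1.054. If losses differ between arms or relate to outcome, there is bias, but the documents give neither the split nor the relation.

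**The case against.** The strongest reply is that *trial* may simply mean the six-month randomized part. The design sentence in the protocol synopsis and section 6, repeated in SAP 5, describes a six-month randomized study with a six-month continuation attached. The protocol's terms are loose elsewhere: the study period lasts only six months, yet protocol 18.2 speaks of its first six months. Table 6 is an operational timeline and does not define an analysis set. Some statistical text is also not readable, including protocol 19.1.8 on supportive analyses. What remains between SAP 7.3 and 7.5 refers to assigning deviations to a phase, so a window for PP may exist in text that cannot be seen.

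This makes the intent arguable, and it stands to that extent. It does not supply the missing limit. No readable text restricts completion, major deviations or steroid use to the study period, and assigning deviations to phases does not say which phases count for PP. If Visit 9 was always meant, the definition still needs to say so.

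Four stronger readings are tempting but unsupported:

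- **That the Auto Mode threshold has no window.** The SAP's usage list ends with a limit to the study period; only protocol 19.1.5 lacks one.
- **That PP is the formal check on non-inferiority.** The documents say only that the endpoints will be evaluated on PP.
- **That the PP result is biased towards HCL.** This requires assuming both an amount of loss and that it falls in the HCL arm. If controls with worse A1C left instead, the shift would go against HCL.
- **That the main conclusion is threatened.** ITT is the primary population.

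**Conclusion.** The point holds as a defect in the definition of a supportive analysis set. Read plainly, the text lets events up to day 365 remove subjects from PP analyses of endpoints that end at day 180. This rests on taking completion to mean Visit 13, which is well supported but not formally stated.

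The size that the documents support is about 2.0%, or 1.4 of 70 per arm and A1C group. It assumes a constant DKA rate at the plan's ceiling and is an illustration, not a forecast. Other continuation losses would add to it by an unknown amount. The primary ITT tests are untouched, and no readable success rule depends on PP. The correction is worth making because the rule as written selects on post-endpoint events for no analytic gain.

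**What to change.** In SAP 7.1.3 and protocol 19.1.5:

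1. Replace *complete the trial* with completion of the 6-month study period (Visit 9).
2. Count major deviations and steroid use for PP only from randomization to Visit 9.
3. Bring the protocol's usage criteria into line with the SAP, which already limits its thresholds to the study period, so that both documents carry one definition.

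Subjects who also complete the continuation can be described separately if that is of interest.

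The cost is a wording change in two documents. Visit dates, exit dates and deviations are already collected, and SAP 7.1.1 already presents subject numbers by period. No new data, visits or clinical rules are needed.

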Transmitter Charger (MMT-7715)	No	No	Dispose or return unused to Sponsor	No
CareLink USB 2.4 GHz (ACC-1003911D)	No	No	Dispose or return unused to Sponsor	No
Ketone Meter	No	No	Dispose	No

Devices may be combined and distributed in kits.

8. Selection of Subjects

Study Population 8.1

A diverse population of patients with type 1 diabetes will be studied. The study population will have a large range for duration of diabetes and glycemic control, as measured by glycosylated hemoglobin (A1C).

Subject Enrollment 8.2

Subjects will be considered enrolled in the study upon signing the Informed Consent/Assent form(s).

Inclusion Criteria 8.3

Subjects will be considered for enrollment in the study if they meet all of the following criteria:

1. Subject is age 2-80 years at time of screening

CEP304 Clinical I				
CEP304DOC	Revision	Н	Page 83 of 182	Medtronic

- a. US, Canada, Australia and New Zealand: Subjects 2-80 years of age will be allowed to enroll in the post approval study.
- b. Europe: Only subjects ≥7 years of age are allowed to enroll in the post-market study.
- 2. Subjects who are 2-21 years are determined by the investigator to have the appropriate, requisite support (family, caregiver or social network) to successfully participate in this study
- 3. Subject must have a minimum daily insulin requirement (Total Daily Dose) of equal to or greater than 8 units/day
- 4. Subjects who are determined by the investigator to be psychologically sound in order to successfully participate in this study.
- 5. Subject has been diagnosed with type 1 diabetes for at least three months

Note: Determination of classification for diabetes will be based on American Diabetes Association Clinical Practice Guidelines accounting for several patient characteristics such as: age of onset, patient's weight or BMI, history of diabetic ketoacidosis, history of therapy management, if available in the medical records.

- 6. Subject must be on one of the following management therapies:
 - Multiple daily injections defined by use of rapid analogue with meals and approved long acting analogue (e.g. detemir or glargine) with or without CGM
 - Insulin pump therapy with or without CGM
- 7. Subject is willing to perform ≥ 4 finger stick blood glucose measurements daily
- 8. Subject is willing to perform required study procedures
- 9. Subject is willing to wear the system continuously throughout the study for at least 80% of the time

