The Study Period: After completion of the run-in period, subjects with CSII therapy (minimum N= 280) will be randomized and placed into one of 2 different arms during the study period:

- 1. The HCL Arm will use the MiniMed system (i.e., using Auto Mode) for 6 months during the study period. There will be N=140 for the HCL arm.
- 2. The Control Arm will use the MiniMed Pump without CGM
 - a. Blinded CGM (Guardian Link (3) Transmitter and Guardian Sensor (3)) will only be worn at baseline, 3 months, and 6 months (two weeks of sensors use). There will be N=140.

Cohort 2: MDI

The Study Period: After completion of the run-in period, subjects with MDI therapy (minimum of N=280) will be randomized and placed into one of 2 different arms during the study period:

- 1. The HCL Arm will use the MiniMed system (i.e., using Auto Mode) for 6 months during the study period. There will be N=140 for the HCL arm.
- 2. The Control Arm will be using their current insulin therapy (MDI).

The Multiple Daily Injection (MDI) subjects will remain on MDI therapy with subjects using their own insulin for 6 months during the study period. The Sponsor will not provide insulin. Blinded CGM (Guardian Link (3) Transmitter and Guardian Sensor (3)) will only be worn at baseline, 3 months and 6 months (two weeks of sensors use). There will be N=140.

MDI subjects who are currently using CGM, i.e. Dexcom or Medtronic Guardian Connect or who are currently using a SMBG alternative, i.e. Libre, will be allowed to enroll in the study and continue using their own device. There will be N=100

Cohort 3: SAP

The Study Period: After completion of the run-in period, subjects with SAP therapy (minimum N=320) will be randomized and placed into one of 2 different arms during the study period. Sensor insertion placement will be according to User guide:

1. The HCL Arm will use the MiniMed system (i.e., using Auto Mode) for 6 months during the study period. There will be N=140 for the HCL arm.

[figure not shown]
This document is electronically controlled *Medtronic Controlled Information* 056-F286, Statistical Analysis Plan Template

- 2. The Control Arm will be using SAP therapy using the MiniMed System.
 - a. The Sensor Augmented Pump (SAP) subjects will use the MiniMed System (SAP without Low Management Suspend on Low, Low Management Suspend before low or Auto Mode) with Real Time CGM for the 6 month study period. There will be N=140.

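### Does the unstated time base for the 80% Auto Mode rule leave the per-protocol set in need of a plan change?

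*SAP*

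**What the plan says.** SAP 7.1.3 makes ITT the primary population and defines the PP set through completion without major deviations, no steroids after randomisation, and several usage rules.

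- **HCL:** Auto Mode at least 80% of the time, and "pump usage (HCL only) of at least 80% and sensor usage (HCL only) of at least 60% during the study period".
- **Sensor-augmented pump controls:** named only in the clause that subjects "have worn the sensor for both Arms (SAP and HCL"), with no percentage of their own.
- **CSII and MDI controls:** "CSII and MDI control arms need to have at least 60% sensor usage during the blinded sensor wear time".

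On use of the set, SAP 7.1.3 adds: "Primary effectiveness endpoints and key secondary endpoints will be evaluated for PP Population".

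Protocol 19.1.5 has a shorter rule. It asks for sensor wear in the Control and HCL arms and 80% Auto Mode use in HCL, with no pump rule and no 60% sensor rule. SAP 7.12, on changes to the planned analysis, records none.

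SAP 5 describes the arms: "The HCL Arm will use the MiniMed system (i.e., using Auto Mode) for 6 months during the study period". For CSII, "The Control Arm will use the MiniMed Pump without CGM". Sensor-augmented pump controls use the system "with Real Time CGM for the 6 month study period". Protocol 8.3, inclusion criterion 9, reads: "Subject is willing to wear the system continuously throughout the study for at least 80% of the time".

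**The concern.** Three things look wrong.

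First, the Auto Mode percentage has no stated denominator. The only period named in that sentence is the study period. Protocol 10.1 places randomisation at its start, while Auto Mode is switched on only at Visit 5. If the clock runs from randomisation, permitted scheduling alone would remove fully adherent late starters, and only from the HCL arm.

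Second, the thresholds look uneven. Sensor-augmented pump controls wear the study sensor for six months, yet they have either no percentage or a borrowed 80%. The second reading would give HCL two sensor thresholds. The pump rule covers HCL alone, although CSII and sensor-augmented pump controls also start the study pump at Visit 3.

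Third, the two documents define the PP set differently and SAP 7.12 does not say so.

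At stake are the PP results for the two co-primary endpoints and for the two non-inferiority key secondary endpoints (margins 2% time below range and 0.4% A1C). Two programmers could build different sets from the same words.

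**Working it through.** The documents state no PP sample size or expected PP fraction in the text shown, so there is no figure of the plan's own to reproduce. The check is schedule arithmetic.

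**Inputs (Protocol 10.3)**

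- Visit 3 is randomisation.
- Visit 4 (V4) is 3–30 days later for subjects with pump experience, and 14–30 days later for HCL subjects without it.
- Visit 5 (V5), when Auto Mode is activated, is 7–21 days after Visit 4.
- Visit 9 (V9) in the HCL arm is day 180 ± 10 after randomisation.

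**Activation day s**

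- Pump-experienced: 3 + 7 = 10 to 30 + 21 = 51.
- No pump experience: 14 + 7 = 21 to 51.

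**Base 1, from randomisation.** Largest share = (V9 − s)/V9. Use needed after activation = 0.80 × V9/(V9 − s). With V9 = 180:

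| s | Largest share | Use needed after activation |
|---|---|---|
| 10 | 170/180 = 94.4% | 84.7% |
| 21 | 159/180 = 88.3% | 90.6% |
| 36 | 144/180 = 80.0% | 100% |
| 51 | 129/180 = 71.7% | unattainable |

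The last start at which a perfect user passes is 0.2 × V9: day 34, 36 or 38 for V9 = 170, 180 or 190.

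**Base 2, from Visit 4**, which Protocol 10.3 labels Day 0. Largest share = (V9 − V5)/(V9 − V4). The worst case is V4 = 30, V5 = 51, V9 = 170: 119/140 = 85.0%. The best is V4 = 3, V5 = 10, V9 = 190: 180/187 = 96.3%. No perfect user fails.

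**Base 3, from activation at Visit 5.** Largest share 100%. No perfect user fails.

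**Base 4, sensor-wear time.** A subject at the 60% sensor floor would need Auto Mode for 0.80 × 60% = 48% of the period, so both percentages do separate work. One caution: HCL subjects in the sensor-augmented pump cohort start the study sensor at Visit 3. Counting their wear before activation would bring back the Base 1 limit.

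**Which base fits the sentence?** Auto Mode doses from sensor glucose (Protocol 7.4). On Base 1, 80% Auto Mode implies about 80% sensor use, so the 60% sensor rule beside it would add nothing. This is not decisive. On Base 3, 80% Auto Mode already implies 60% sensor use over 180 days for starts up to day 45 (0.80 × 135/180 = 60%). For a day-51 start it implies only 0.80 × 129/180 = 57.3%, so there the sensor rule can still bind.

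Nor does the SAP 5 description of six months of Auto Mode fix the clock. The earliest activation leaves 170 of the 180 days, so that sentence describes the arm loosely and cannot be a denominator.

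**The case for a change.** The strongest case for a change is that the PP set is prespecified for the non-inferiority endpoints, where PP results carry more weight than in a superiority comparison. A denominator picked after the data are seen would be a post hoc choice acting on one arm. The wording could be tightened in a few sentences with no new data, since subjects are to upload at least weekly (Protocol 8.3). All of that is fair. The arithmetic is also right, the Auto Mode denominator is not stated in the text shown, and the two PP texts do differ.

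What does not stand is the step from there to a needed amendment. The exclusion of perfect users appears only when counting from randomisation, and the text does not commit to that. Protocol 10.1 gives partial support by randomising at the start of the study period, but it also places Visit 3 inside the run-in.

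The natural remedies would go beyond clarification. A pump-use cut for CSII and sensor-augmented pump controls, or a 60% sensor cut for the latter, has no source in either document. A PP set may reasonably test adherence to the investigated therapy. Inclusion criterion 9 concerns willingness at enrolment and does not define adherence.

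The mismatch between documents is largely bookkeeping. The SAP divides the protocol's control arm into its three cohorts and adds usage floors. SAP 3.0 was written to protocol version G, and the listed changes for version H name none to the PP set. An entry in SAP 7.12 would alter no result.

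**Conclusion.** No change to the plan follows. The gap is a definition not written out, in the text shown, for a population that is not primary. An analyst specifying the PP dataset would be expected to count Auto Mode use over time in which it could be used, and on that base no adherent subject is lost to scheduling. For sensor-augmented pump controls, the literal reading, sensor worn with no percentage, can be programmed as it stands.

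On the one troublesome base the limit is exact: activation after day 36 (34–38 across the Visit 9 window) within a permitted range ending at day 51. How many HCL subjects fall there depends on visit dates the documents do not give, so neither the share affected nor any bias can be computed. ITT is unaffected. The success rule in Protocol 19.1.6, that both co-primary tests must be met at one-sided 0.025, is not tied to the PP set in the text shown.

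Two assumptions support this. The denominator is settled when the dataset is specified, before PP results are examined. The statistical pages that are not public, including parts of SAP section 7 and Protocol 19.1, contain nothing that fixes the randomisation base; they may well define usage outright.
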